2. INTRODUCTION AND BACKGROUND

2.1 Background Information

Renal transplantation is considered to be the best treatment option for patients with end stage kidney disease in terms of quality of life and survival outcomes, as well as relative cost efficiency compared to dialysis.(1) Transplant recipients are susceptible to wound complications, arguably the most common post-transplant surgical complication, which may contribute to an additional risk of graft rejection or failure, prolonged length of stay, readmission and re-operation, as well as increased treatment costs. (2)

Wound complications have been previously superficial or deep dehiscence and/or infection, perigraft collections or seromas, cellulitis, lymphocoeles, and prolonged wound drainage. Studies have shown that the most important risk factors for wound complications in transplantation are immunosuppression and obesity (3). The incidence of wound infection in the presence of immunosuppression is approximately 7%, and more potent immunosuppressive agents are thought to result in a higher incidence of wound complications. (4) Comparing patients with high (>30) and low BMI (<30) patients, meta-analyses have demonstrated a significantly higher risk of wound infection (RR = 3.13, CI, 2.08–4.71; P <0.001), and wound dehiscence (RR 4.85, CI, 3.25–7.25; P <0.001). (5)(6)

Other relevant factors in renal transplantation include surgical technique and expertise, reoperative procedures, the presence of a haematoma, as well as recipient comorbidities such as advanced age, diabetes, malnutrition, dialysis (haemo- and peritoneal), and prolonged uraemia. The surgical closure technique of the incision, in particular, the precise closure of defects in each layer, has also been identified as an independent factor in reducing wound complications. (7) (8)

Negative pressure wound therapy (NPWT) utilises a foam sponge, in combination with a semipermeable adhesive dressing and a vacuum pump device to increase blood flow, drain fluid and exudate, and contract wound edges. Meta- analyses have suggested that when compared to standard wound dressings on closed incisions, NPWT significantly decreases wound size and healing time, with a significant reduction of risk of surgical site infections (RR=0.54, p= 0.01), and a significant reduction in risk of seroma formation (RR=0.48, p=0.01). (9) (10) (11).

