2.2 Research Question

In patients undergoing a renal transplant (RT), does the application of negative pressure wound therapy (NPWT) with a Prevena Incision Management System (Prevena) immediately to the closed wound at the end of the renal transplant operative procedure result in fewer wound complications, when compared to standard adhesive, waterproof dressings (SD)?

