4.2 Study Design

Ethics approval will be obtained from SLHD-RPA by the Lead site at RNSH. All sites will require Governance approval prior to study commencement. Enrolled participants in this study will present for renal transplantation at a participating study site, having received routine planning and workup for the operation which will include education regarding the trial, and providing informed consent at the time of admission for the operation. Study investigators will register the patient in an online database (REDCap Database Vanderbilt University) controlled by the study investigators, which will randomly allocate the patient to a treatment arm, to be revealed after transplantation and during the closure procedure (closure defined as closure to the muscle, subcutaneous tissue or skin). Patient data variables including demographic data, medical comorbidities and pathology results will be recorded from the patient electronic medical record (see appendix). Details of the donor kidney will be also be recorded, including donor demographics, anatomical characteristics, ischaemic time, and time of retrieval.

The patient will be prepared for surgery as per site specific protocols; variables to be recorded include peri operative antibiotic administration and skin preparation (application of an antiseptic agent such as chlorhexidine or iodine, or iodine impregnated drapes). Each surgeon will proceed with the procedure of renal transplantation as per operator preference. Operative details to be recorded include site and side of incision (Rutherford-Morrisson), warm ischaemic time, time of reperfusion, operation duration, estimated blood loss, length of incision, and method (materials; eg. sutures, staples) of closure in layers (muscle, subcutaneous tissue and skin). Drain presence and placement is also recorded. Bilateral renal transplants and bilateral incisions will be counted as one incision and will allocated to the same treatment arm as one entity.

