4.4 Study sites

The study sites are Royal North Shore Hospital, Royal Prince Alfred Hospital and Westmead Hospital, located in Sydney, Australia. Outside the confines of this research protocol, surgeons at each site will perform the renal transplantation as per their own procedural methodology, and perioperative management will be as per site specific protocol and guidelines.

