5.4 Enrolment and Randomisation Procedures

All patients presenting for a renal transplant over a 24 month period at one of the participating sites will be eligible for enrolment in this study. Patients who sign the Participant Information Sheet and Consent Form (PISCF) and fulfil all inclusion and exclusion criteria, as well as compliance with contraindications listed in the Prevena IFU, will be considered eligible for study participation. Participants may recruited at any point prior to surgery once surgery is confirmed, ideally at the time of admission to hospital for the procedure, or if this is not possible, at the time consent is obtained for the surgery. A unique study identification number is then assigned to enrolled participant by the study investigators.

Participants who signed the PISCF but do not fulfil all inclusion and exclusion criteria, IFU related indications and contraindications, hospital standard of care tests, or who withdraw informed

consent prior to the procedure are screen failures. They will be documented on the screening and enrolment log with the screening failure reason. For the purposes of analysis, an Intention to Treat (ITT) sample will be based on all enrolled subjects, and a secondary as per-protocol analysis will be based on all patients who have the intervention of having a dressing placed on the closed incision following renal transplant.

Patient registration will occur prior to surgery on an online research database (REDCap; Vanderbilt University, Nashville, USA) hosted at Royal North Shore Hospital (19). Randomisation via REDCap will occur when the patient fulfils all intra-operative exclusion criteria and after commencement of skin closure (defined as closure to the muscle, subcutaneous tissue and skin). Randomisation will be stratified by site, with block randomisation by variable block size in a 1:1 ratio. , The surgical team, clinical staff, and patient will not be blinded to the intervention status.

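### The arm may be revealed before the last skin layer is closed, so an unblinded surgeon may finish closure knowing it: a minor, avoidable performance-bias route

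*Combined protocol and SAP*

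**What the plan says.** Two sections set the timing, and they differ.

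- Section 5.4 registers the patient before surgery and randomises in REDCap once the intra-operative exclusions are cleared and "after commencement of skin closure (defined as closure to the muscle, subcutaneous tissue and skin").
- Section 4.2 describes REDCap allocating the arm at registration, "to be revealed after transplantation and during the closure procedure (closure defined as closure to the muscle, subcutaneous tissue or skin").

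Section 5.4 adds: "The surgical team, clinical staff, and patient will not be blinded to the intervention status". On technique, section 4.4 says that "surgeons at each site will perform the renal transplantation as per their own procedural methodology".

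Section 2.1 states that "precise closure of defects in each layer, has also been identified as an independent factor in reducing wound complications". Section 4.6 puts infection, dehiscence and fluid collection within 30 days into the primary outcome. Appendix A counts separation of skin and subcutaneous tissue without documented infection as superficial dehiscence.

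Section 4.2 records "method (materials; eg. sutures, staples) of closure in layers (muscle, subcutaneous tissue and skin"), together with "operation duration, estimated blood loss, length of incision". Section 2.2 describes the device as applied "immediately to the closed wound at the end of the renal transplant operative procedure".

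**The concern.** Randomisation balances what happens before it. Anything the surgical team does after learning the arm can differ between arms. Here the step still unfinished at the reveal is part of wound closure, which the protocol itself treats as prognostic for wound complications. If surgeons closed more carefully, or less so, when they knew which dressing would follow, part of any difference between arms would come from closure and not from the device.

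The safeguards in the plan act elsewhere. The blinded photographs and imaging in section 5.5 protect assessment. The statement in section 4.2 that management is otherwise identical sets no rule for closure. The closure record covers materials by layer but not precision. Appendix C, to which sections 6 and 7 refer for the data collected, is not in the text available for this review, so whether more is captured cannot be checked.

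**Working it through.** **Step 1: what the wording permits.** Section 5.4 sets a lower limit, the start of skin closure. On its natural reading only part of the skin is left to close, although its bracket stretches the term to muscle, subcutaneous tissue and skin. Section 4.2 joins the same layers with *or*, so a reveal at the muscle layer would also comply. Neither section sets completion of the last layer as a condition. Sites could work to different timings and all comply.

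**Step 2: the plan's own figure.** Section 9.1 uses 15% v 7%, two-sided alpha 0.05, power 80% and no continuity correction:

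N = {1.96 × √(0.11 × 0.89 × 2) + 0.84 × √(0.15 × 0.85 + 0.07 × 0.93)}² / 0.08² = 238.7, so 239 per arm. This reproduces. At 250 per arm the power is 81.8%. Moving randomisation changes none of these inputs.

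**Step 3: audit dehiscence.** Section 9.1 gives 5% at site 1 (60 transplants a year) and 18% at site 3 (100 a year). For site 2 (90 a year) it gives an 8% infection rate and no dehiscence figure. Counting site 2 as zero:

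(60 × 5% + 90 × 0% + 100 × 18%) / 250 = 21 / 250 = 8.4%.

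The audit does not separate superficial from deep dehiscence. On the skin-only reading only part of the 8.4 points is exposed, so the full 8.4 is a maximum for that reading with site 2 at zero.

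**Step 4: illustration.** The assumptions, none of them from the documents, are a 10% relative shift in the exposed dehiscence in one arm and an exposed share of a quarter, half or all of 8.4 points. All other components are unchanged.

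Change in the composite = share × 8.4 × 10% = 0.21, 0.42 or 0.84 points.

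The chance of a significant result in the stated direction is 1 − Φ((1.96 × s0 − d) / s1). Here d = p1 − p2, s0 = √(2 × p̄ × (1 − p̄) / 250) with p̄ the mean of p1 and p2, and s1 = √((p1(1 − p1) + p2(1 − p2)) / 250).

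Worked case, half exposed:

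- No device effect, 15% v 14.58%: d = 0.0042, s0 = s1 = 0.03175, giving 1 − Φ(1.96 − 0.132) = 3.4%.
- Planned effect with control-arm dehiscence lowered, 14.58% v 7%: d = 0.0758, s0 = 0.02775, s1 = 0.02754, giving 1 − Φ(−0.777) = 78.2%.

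| Exposed share | Shift (points) | No device effect: significant in shifted direction | Power at planned effect, control arm lowered |
|---|---|---|---|
| None | 0 | 2.5% | 81.8% |
| Quarter | 0.21 | 2.9% | 80.0% |
| Half | 0.42 | 3.4% | 78.2% |
| All | 0.84 | 4.5% | 74.1% |

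**The case against.** The plan already narrows this route. Randomisation is in theatre, after the intra-operative exclusions and after skin closure has begun, so on the section 5.4 reading little is left to do. That wording is also only a lower limit and does not stop a site from randomising once the skin is closed. Section 2.1 says that closure is prognostic. It does not say that finishing part of the skin layer while knowing the dressing changes risk. Technique is left to the operator in both arms, and closure materials are recorded. All of this stands, and it is why the point is minor. It does not remove the route, because nothing requires the reveal to wait.

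An objection on cost also stands in part. A later reveal means a wait under sterile conditions, of a length the documents do not give. Drain placement is stated only under the intervention arm in section 4.2, so it too must fit the new timing. Since section 5.4 already has drains checked as an intra-operative exclusion before randomisation, this adds little.

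A reader might infer three stronger things that the documents do not support:

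- That closure will differ by arm, or that the bias favours Prevena. Nothing shows either.
- That deeper layers will routinely be open at the reveal. This rests on one word in section 4.2, which conflicts with the more specific randomisation section.
- That the exposed outcome is larger than 8.4 points, by counting site 2's whole upper complication rate as dehiscence. Section 9.1 reports infection there, not dehiscence.

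**Conclusion.** The point holds as a minor one. The text lets an unblinded surgeon finish closure knowing the arm, and sections 4.2 and 5.4 disagree on what closure means. The result is a performance-bias risk whose size and direction the documents do not give, probably small if only part of the skin remains open.

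The table in the working shows only what a 10% shift would do under assumed exposed shares; it does not estimate what will happen. Its one practical message is that the margin above 80% power is narrow (250 enrolled against 239 needed), so even a small dilution would use it up. The point does not call the sample size or the validity of the trial into question.

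**What to change.** Use one definition of closure and one rule in both 4.2 and 5.4: patients are registered in REDCap before surgery; randomisation is performed, and the allocation revealed, only after the final skin layer is closed and the intra-operative exclusion criteria have been checked and logged. This also settles whether the arm is generated at registration or in theatre. Report the recorded closure method by layer and by arm as a descriptive check.

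The cost is a shared sentence and definition, plus a short wait under sterile conditions between final closure and the dressing. The step already takes place in theatre, so it is moved and not added, and the dressing goes on a closed wound in any case. No patients, visits or sample-size inputs change. The drain statements in sections 4.2 and 5.2.3 must be reconciled with each other and with this timing; how is for the investigators to decide. The change closes this route only: postoperative care remains unblinded.

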5.5 Blinding Arrangements

Study investigators will be partially blinded, as surgical proceduralists and treating clinical staff will be unable to be blinded due to the visually distinct difference between a Prevena and standard dressing. Study investigators will be able to identify the allocated treatment within 7 days due to active intervention and likely at 14 days due to ongoing clinical contact. However, wound assessment at Day 7 and Day 14 (as well as Day 30 and 90) will include a photo of the wound by a study investigator once the dressing is removed, for independent blinded assessment by the designated wound assessor for each site (or alternative site for Day 30 and 90 photos); this is done to improve the validity of assessment. Blinding will occur at Day 30 and 90 follow up for imaging staff and the designated independent wound assessor for each site, who will not be informed of the allocated treatment arm. Patients will be instructed to not disclose this information to the wound assessor or imaging staff.

5.6 Participant Withdrawal

5.6.1 Reasons for withdrawal

Patients may withdraw from the study at any point, but will continue to be followed up and managed as per routine practice. Patient withdrawal may also occur due to loss of follow up, adverse event or death. Investigators may withdraw the patient from the study once the patient has been randomised, if the Investigator believes the allocated treatment arm is not in the patient's best interests, or the patient meets IFU related contraindications, however the reasons for withdrawal must be clearly documented.

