The intervention arm will have the closed incision dressed with the Prevena Incision Management System (Kinetic Concepts Inc, San Antonio, TX, USA), a portable NPWT device, utilising a foam interface containing 0.019% ionic silver. The Prevena is preset to a continuous vacuum suction at 125mmHg. The Prevena device of appropriate size is to be applied under sterile conditions at the time of closure of the incision, with drain placement to be >10cm from the wound edge. The device should remain intact for a total of 7 days, at which point it will be removed. The wound will be inspected by a study investigator for evidence of a wound complication. A dressing may be reapplied, including a Prevena dressing if thought clinically indicated by the presence of a wound complication.

Postoperative ultrasound of the grafted kidney may be performed by peeling back the adhesive component of the Prevena dressing, and the Prevena can be subsequently reinforced with an adhesive dressing to establish adequate seal, with suction reinitiated within one hour if lost. If the wound edge is exposed, the Prevena device is inadvertently removed during ultrasound or clinician concern regarding the wound or device results in removal of the Prevena device earlier than planned, the device can be replaced at investigator discretion, however these details must be documented in the database. The patient will continue in the intervention arm as per principles of intention to treat regardless of whether the Prevena is replaced.

The control arm will have the closed incision dressed with a standard waterproof, adhesive dressing at the operator's discretion. This will not be controlled, but the type of dressing used will be recorded. This dressing will remain intact for a minimum of 7 days and may be changed thereafter as per site specific practices, which will be documented.

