5.6.2 Handling of withdrawals

[figure not shown]
All participants withdrawn will ideally complete all study visits including Day 30 follow-up if able, as per routine clinical practice. Withdrawn patients will be included in an intention to treat analysis.

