9 STATISTICAL METHODS

9.1 Sample Size Estimation

Wound infection rate have been estimated between 5 and 30% based on a current literature, including a systematic review and meta-analysis.(3)(10) Weighting the participating site's preliminary audit data by expected enrolment rates, the average wound complication rate was estimated to be 15%. NPWT has been suggested to offer an approximate 46% reduction in wound infection rates for abdominal incisions (3)(10).

Based on a two-sided type one error of $\alpha = 0.05$ and a type two error of $\beta = 0.2$ (corresponding to a power of 80%) a total sample size of 239 patients per group (478 in total) is needed to evaluate primary

endpoints, which was calculated using the power formula for a chi-square test without Yates' continuity correction due to the large sample size and binary dependent variable (22). Accounting for potential loss to follow up, which is estimated to be minimal, as every patient receiving a kidney transplant is planned to follow up every day for 30 days postoperatively, the sample size has been rounded up to 250 per arm (500 total). Missing data from patients who fail to have endpoints recorded will be treated on an intention to treat basis with last observation carried forward.

Estimated mean wound complication rate in control arm across 3 sites : 15%

Site 1 : 5-10% (60 transplants per year, audit data demonstrates 5% dehiscence rate)

Site 2 : 8-15% (90 transplants per year, audit data demonstrates 8% infection rate)

Site 3 : 18-25% (100 transplants per year, audit data demonstrates 18% dehiscence rate)

Conservative estimate of treatment effect: ~50% reduction in all wound complications with closed incision NPWT over lower abdominal/groin wounds (Rutherford Morrison) in high risk population.

Estimated complication rate for Prevena arm (intervention) = 7%

Dichotomous Endpoint, Two Independent Sample Study

Sample Size	
Group 1	239
Group 2	239
Total	478

Study Parameters	
Incidence, group 1	15%
Incidence, group 2	7%
Alpha	0.05
Beta	0.2
Power	0.8

$$N_1 = \left\{ z_{1-\alpha/2} * \sqrt{\bar{p} * \bar{q} * \left(1 + \frac{1}{k}\right)} + z_{1-\beta} * \sqrt{p_1 * q_1 + \left(\frac{p_2 * q_2}{k}\right)} \right\}^2 / \Delta^2$$

$$q_1 = 1 - p_1$$

$$q_2 = 1 - p_2$$

$$\bar{p} = \frac{p_1 + k p_2}{1 + K}$$

$$\bar{q} = 1 - \bar{p}$$

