9.3 Statistical Analysis Plan

Statistical analysis will be pre-specified and conducted according to both principles of intention to treat and per-protocol analysis, using SPSS version 20 (IBM, Armonk, NY, USA). Each incision will be randomized to the Prevena or standard dressing group. In the case that a patient requires bilateral incisions, both incisions will be allocated to the same treatment arm and counted as a single incision. Baseline characteristics of the two groups will be recorded and compared using Student's t-test and chi-square test for continuous and discrete data respectively. The primary outcome, the proportion of wound complications, will be compared between the Prevena and standard dressing groups using a chi-square test without Yates' continuity correction with a two-sided alpha of 0.05 at the final analysis using the Peto approach to preserve the overall significance level of 0.05 (23). An absolute risk increase/reduction for wound complications will be presented for the use of Prevena, as well as the number needed to treat in order to prevent specific wound complications. Patients lost to follow-up will be used in an intention-to-treat analysis with last observation carried forward.

The secondary outcome of identification of risk factors for wound complications will be assessed by multiple logistic regression of collected variables to assess their odds ratio. To prevent overfitting with the selected sample size, variables will be stepwise selected and also assessed for multicollinearity with the significance level of the dependent variables adjusted for multiplicity. Secondary outcomes will be compared between groups using a chi-square or Fisher's test for reoperation rate and delayed graft function and t-test for continuous variables, including the pain scale and quality of life. Non-normally distributed continuous variables will be tested for and compared using the Mann-Whitney *U* test. Survival analysis will be performed for allograft survival time with subjects without events censored at the 90 day final observation. A *p* value of less than 0.05 will be considered significant for the secondary outcomes and all tests will be two-sided.

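### An investigator who knows the arm may withdraw a randomised patient from the study, and the 30-day outcome may then go unobserved and be counted as no event

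*Combined protocol and SAP*

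**What the plan says.** Section 5.6.1 (Reasons for withdrawal): "Investigators may withdraw the patient from the study once the patient has been randomised, if the Investigator believes the allocated treatment arm". The test is whether that arm serves the patient's best interests; meeting an IFU contraindication is a second ground. The reason must be documented. The same section groups other events under withdrawal: "Patient withdrawal may also occur due to loss of follow up, adverse event or death".

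Section 5.6.2 (Handling of withdrawals): "All participants withdrawn will ideally complete all study visits including Day 30 follow-up if able, as per routine clinical practice". It adds: "Withdrawn patients will be included in an intention to treat analysis".

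Section 5.4 says that the surgical team, clinical staff and patient are not blinded. Section 5.5 says that study investigators can identify the arm within 7 days, and probably at Day 14.

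On missing outcomes, section 9.1 says: "Missing data from patients who fail to have endpoints recorded will be treated on an intention to treat basis with last observation carried forward". Section 9.3 says: "Patients lost to follow-up will be used in an intention-to-treat analysis with last observation carried forward".

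For early removal of the Prevena device, section 4.2 has a different rule: "The patient will continue in the intervention arm as per principles of intention to treat regardless of whether the Prevena is replaced".

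**The concern.** Section 5.6.1 does not distinguish stopping the allocated dressing from leaving the study. The decision is made with knowledge of the arm and, on the best-interests ground, because of it. After that, nothing requires the 30-day primary outcome to be collected.

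Inclusion in the intention-to-treat analysis keeps the patient in the denominator but does not supply the outcome. Carrying the last observation forward keeps a complication already recorded, but turns an event-free status into no event at 30 days. A patient withdrawn before any wound assessment has nothing to carry forward, and the plan does not cover that case. Section 9 names no sensitivity analysis for missing outcomes.

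The loss could run either way. The IFU ground bears mainly on Prevena, and missed events there would favour the device. The best-interests ground applies to both arms, and missed events mainly among controls would hide a real benefit.

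**Working it through.** **The plan's own figure.** Section 9.1 assumes 15% v 7%, two-sided alpha 0.05, 80% power and no continuity correction:

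N = {1.96·√(0.11·0.89·2) + 0.84·√(0.15·0.85 + 0.07·0.93)}² / 0.08² = 239 per arm.

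This reproduces. Rounding up to 250 leaves 11 patients per arm (11/250 = 4.4%) for loss. Power at 250 per arm is 81.8% by the normal approximation and 82.4% by exact enumeration.

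**Model for the loss.** An uncaptured event in a withdrawn patient counts as no event, so

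observed rate = true rate − f·r·(1 − c),

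where f is the share of the arm withdrawn, r the event risk in those patients, and c the share of their events that is captured. All three are assumptions; the documents give none of them. Example: f = 5%, r = 30%, c = 0 gives 15% − 0.05·0.30 = 13.5%.

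The results below enumerate two binomials exactly, with 250 per arm and the uncorrected chi-square test (|z| > 1.96).

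**Chance of a false finding for Prevena, true rate 15% in both arms (2.50% with no loss)**

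| Withdrawn | Risk r | c = 0.75 | c = 0.5 | c = 0 |
|---|---|---|---|---|
| Prevena 2% (5 patients) | 30% | 2.79% | 3.10% | 3.83% |
| Prevena 2% | 15% | 2.64% | 2.79% | 3.10% |
| Prevena 5% (about 12 patients) | 30% | 3.27% | 4.24% | 6.93% |
| Prevena 5% | 15% | 2.86% | 3.27% | 4.24% |
| Prevena 5%, control 2% | 30% | 2.94% | 3.46% | 4.74% |
| Equal in both arms | 30% | 2.50% | 2.50% | 2.50% |

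**Power at 15% v 7% (82.4% with no loss)**

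| Withdrawn | Risk r | c = 0.75 | c = 0.5 | c = 0 |
|---|---|---|---|---|
| Control 2% | 30% | 81.2% | 79.9% | 77.1% |
| Control 5% | 30% | 79.2% | 75.6% | 67.3% |
| Control 2% | 15% | 81.8% | 81.2% | 79.9% |
| Control 5% | 15% | 80.8% | 79.2% | 75.6% |
| Both 2% | twice each arm's rate | 82.0% | 81.5% | 80.6% |
| Both 5% | twice each arm's rate | 81.3% | 80.2% | 77.8% |

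A normal approximation agrees where the two overlap: for 5% one-sided loss at 30% risk and no capture, it gives 6.9% for a false finding for Prevena (Prevena loss) and 67.0% power (control loss).

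**Which part of the outcome is exposed.** The primary outcome in section 4.6 is infection, dehiscence or fluid collection within 30 days. Complications that bring a patient back are recorded under section 4.2. Withdrawal most endangers what the remaining study visits add: blinded review of photographs not yet taken (section 5.5), and the Day 30 ultrasound, which the schedule in section 6 marks as study-specific. The scan matters only so far as collections found by it alone count. Appendix A starts from clinical suspicion and uses imaging to confirm, whereas section 4.2 expects the Day 30 scan to find deep complications.

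**The case against.** The best case for the plan is that little is left to lose. Withdrawn patients stay in the analysis, and Day 30 is named as a visit to complete. IFU contraindications are screened before randomisation (section 5.4), so that ground covers mainly those that emerge later or were missed. Randomisation happens during closure and the device stays on for 7 days, so there is little time to object to the arm. Section 4.2 already keeps in the arm a patient whose Prevena is removed early for clinician concern. Section 9.1 expects minimal loss because "every patient receiving a kidney transplant is planned to follow up every day for 30 days postoperatively". The provision protects patients, and the no-event imputation comes from the missing-data rule, not from section 5.6.1. The largest figures need about 12 withdrawals in one arm only, doubled risk, and no event captured. A figure under the 5.6.2 heading could not be read and may add detail.

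Most of this stands as a limit on size. The zero-capture column is an outer bound, since a complication recorded before withdrawal is kept. But daily follow-up is offered as a reason to expect little loss, not as a rule for withdrawn patients, and it need not replace the blinded photographs or the study scan. The section 4.2 rule does not settle the matter either: the same clinical worry can be handled under 4.2 by one investigator and under 5.6.1 by another. The fix below does not alter last observation carried forward; it reduces the number of outcomes that rule has to fill.

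**Conclusion.** The concern holds. A written rule lets a decision made with knowledge of the arm determine whether a 30-day primary outcome is observed, and it sits badly with section 4.2.

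The size is conditional on assumed withdrawal, risk and capture. At about 2% withdrawal with good capture it is negligible: a 2.6% to 2.8% chance of a false finding for Prevena against 2.5%, or about 81% to 82% power against 82%. It becomes material only at about 5% in one arm with poor capture, reaching at worst 6.9% and 67% in the cases computed. Equal withdrawal leaves the false-positive rate unchanged and costs some power. The documents do not establish the direction. The change is worth making because it is cheap and because outcomes not collected may be unrecoverable later; confidence that the effect matters in practice is moderate.

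**What to change.** In section 5.6.1, define two separate events.

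1. **Allocated dressing stopped or changed.** The investigator may do this at any time in the patient's interest, for an adverse event or for an IFU contraindication, and records the reason. The patient stays in the study and in the allocated arm, as under section 4.2.
2. **Withdrawn from study.** Only by the patient withdrawing consent, never on the investigator's initiative because of the arm.

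Record death and loss to follow-up as categories of their own.

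In section 5.6.2, require that patients whose dressing is stopped or changed complete all scheduled assessments, including the Day 30 photograph and ultrasound. For those who decline visits, take the 30-day outcome from the medical record where consent allows. Report dressing stops, withdrawals and missing Day 30 assessments by arm.

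The cost is amendment wording, plus a line in the consent form if record access after withdrawal is not already covered (the consent pages were not available to check). Clinicians remain free to change treatment, the sample size stays at 250 per arm, and the visits are already planned for every patient. The downside is some effort to keep these patients attending.
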